8.3 Stimuli

None

8.4 Prior to Runs

Recruitment material will be disseminated via company email and safety newsletters.

Interested participants will be asked to contact a research coordinator to confirm their interest and eligibility. If the participant is interested and eligible, the research coordinator will send a copy of the consent form via email for the participant to review and then schedule a time at least 24 hours later for a designated member of the research team to review the informed consent and study procedures with the participant. Informed consent will be completed by the principal investigator or a designated member of the study staff. As pilots could be based in many locations across the country, informed consent will be completed either by phone, video conference, or in person. If the informed consent session is not conducted in-person, DocuSign will be used to obtain the participant's signature and an electronic copy of the signed consent will be emailed to the participant. If the informed consent session is conducted in-person, a paper copy with wet ink signature may be collected and a photocopy will be given to the participant.

8.5 Experiment Design

We will collect objective and subjective sleep, sleepiness, workload, and performance data from on-duty pilots during the aforementioned short-haul flight operations. Data will be collected during days off prior to the trip start, during flights, and during days off following the flight operations. Each pilot will collect data during at least two trips.

8.6 Data Protection

Types of Data. Several questionnaires and PVT tests will be collected using the iPod app. All of the questionnaires are included in the supplemental material submitted with this protocol. We will not collect any personally identifying information using the app. We will collect the participant's name, e-mail address, phone number, and preferred mailing address solely for the purposes of conducting the study (i.e., to coordinate mailing the study devices and to provide compensation, if applicable).

Data Management/Storage. To ensure that individual crew data remains confidential, participants will be allocated an individual numerical code. All data will be collected using this code and not the individual's name or other identifiable information. The data sheet linking names and codes will be stored on an encrypted hard drive following NASA IT security rules.

Coded study data will be stored on devices provided by each airline and/or their research partner (Delta Airlines partners with [name] at Brigham and Women's Hospital; United Airlines partners with [name] at Washington State University). Coded data from all airlines will be archived and aggregated at Washington State University for processing and analysis. Data access will be limited to personnel named on this protocol. NASA researchers will access study data either via computers provided by the airlines or their research partners or via encrypted VPN. The results of the research will not be presented in any form that identifies individuals.

The data will not be used to make employment measures or decisions with respect to individuals.

Participant Withdrawal. Participants who choose to withdraw their consent may do so at any time. Any partial data that has been collected will be considered for analysis unless the participant requests that their data be deleted.

9. Proposed Test Schedule

The study will take place over an estimated one-year period. Each participant will collect data during two trips lasting 2-7 days each, with up to 3 days of off-duty data collection before and after each trip, for a total data collection of up to 26 days per pilot.

Pre-study Questionnaires

Once consented, participants will be provided with instructions regarding the study procedures and equipment (i.e., an iPod with the NASA PVT+ application, an Actiwatch, and a light and temperature sensor). Equipment will be either be mailed to the participant or available for collection from a designated staff member. Participants will then complete a series of baseline questionnaires including a demographic questionnaire, performance questionnaires, a baseline exercise questionnaire, the Morningness/Eveningness Questionnaire (MEQ), the Epworth Sleepiness Scale (ESS), the Pittsburgh Sleep Quality Index (PSQI), the Insomnia Severity Index (ISI), and the NASA Task Load Index (TLX), using the NASA PVT+ app. Participants will also complete a practice sleep diary and a practice PVT in order to ensure that they understand the study procedures. Demographic information, including age, flight experience, living arrangements, and the results of the aforementioned questionnaires will be used as covariates in data analysis as each of these factors can influence sleep and performance.

Procedure

Participants will begin data collection 1-3 days prior to their trip departure (depending on the participant's availability and off-duty time between trips). Data will be collected using the NASA PVT+ App and the Actiwatch. Participants will begin wearing the Actiwatch and continue to wear it for the duration of the study period which will conclude up to 3 days following their return from their trip. They will make entries in the App reporting on their sleep periods at the beginning and end of each day, including days off. Participants will also have additional entries during flight duty periods.

A study staff member will check in (e.g., via phone call) regularly to remind the participant to complete the study tasks and to answer any additional questions.

Details are outlined below as well as summarized in Table 2 and Figure 3. Full details can be found in supplemental documents.

Return of equipment. Participants will be provided with either a return pre-paid box or instructions on where to return the equipment to a designated staff member. Data will be downloaded, cleared, and a study ID reset on each device before sending to another participant. Data collected on iPod and actiwatch devices will only be identified by an ID code. No identifying information will be collected during the study period.

Morning Sleep Diary. At the beginning of each day, participants will complete a sleep diary within the NASA PVT+ App. Each entry will include: wake-up time, a rating of sleep quality (5 -point scale from Extremely Good to Extremely Poor), the Samn-Perelli (SP) and Karolinska Sleepiness Scale (KSS), the location of their sleep, the timing and duration of any awakenings during the sleep period, and any additional information (i.e., notes).

Evening Sleep Diary. At the end of each day (right before sleep), participants will use the App to report the time they are going to sleep, the location of their sleep (e.g., home, hotel), if they used any caffeine during the day (amount used), any naps during the day (including timing and duration), timing/type of meals, and timing/type of exercise. Participants will also complete the SP and KSS and have an opportunity to provide any additional information about the day if necessary.

Flight Duty Period Data Collection. On flight duty days, participants will have additional entries and tasks to complete within the NASA PVT+ App (i.e., pre-duty, during flight, post-flight, and post-duty). Pre-duty entries will include: flight information, layover information, commute information, caffeine intake, the SP and KSS, and the Psychomotor Vigilance Task (PVT). During their flight, they will complete the SP, KSS, and the PVT, at or near the timing of TOD. Post-flight entries will occur within one hour of landing and will include flight information, the NASA TLX, report of fatigue countermeasures used, and hassle factors experienced (e.g., weather, air traffic control issues, traffic), SP, KSS, and PVT (if needed). Post-duty entries will include: duty information, operational factors (e.g., delays, sit times), overall fatigue rating (visual analog scale), KSS, SP, and PVT. Participants will also complete both the morning and evening sleep diary entries on flight duty days. Additional questions in the evening sleep diary on duty days include: commute information (i.e., timing, duration, and type of travel).

Table 2. Timing of data collection (repeated for one circadian-disruption trip and one trip without circadian disruption)

	1-3 Off-duty Days	Each Day of the Trip	1-3 Off-duty Days
Morn/evening Sleep Diary	✓	✓	✓
Sleepiness/ Fatigue	✓	✓	✓
Performance	✓	✓	✓
Workload		✓	
Duty information		✓	

[figure not shown]

Figure 3. Timing of flight day data collection

Tests and Scales

Morningness/Eveningness Questionnaire (MEQ). The MEQ is a widely used self-assessment questionnaire (19 items) designed to determine a person's chronotype, that is, whether they experience peak alertness in the morning, evening, or in between.

Pittsburgh Sleep Quality Index (PSQI). The PSQI is used to measure sleep quality in adults over the last month. The scale is broken down into 7 Components, which include: subjective sleep quality, sleep latency, sleep duration, habitual sleep efficiency, sleep disturbances, use of sleeping medications, and daytime dysfunction. Higher scores indicate poorer sleep quality.

Insomnia Severity Index (ISI). The ISI is a 7-item questionnaire used to assess the severity of daytime and nighttime components of insomnia. The scale uses a 5-point Likert scale to measure the different components, including: severity sleep onset, sleep maintenance, early morning awakening problems, sleep dissatisfaction, interference of sleep difficulties with daytime function, noticeability of sleep problems by others, and distress caused by the sleep difficulties. Total score can range from 0-28 with higher scores indicating more severe insomnia.

Epworth Sleepiness Scale (ESS). The ESS is a routinely used self-administered questionnaire (8 items) that can be used to assess daytime sleepiness.

NASA-TLX. The NASA Task Load Index (TLX) is a subjective, multidimensional tool that rates workload relative to a task. The TLX is taken at the start of the study to make a series of pairwise comparisons and then again for rating each flight period.

Hassle Factors. Factors that may affect workload during flight operations (e.g., weather, air traffic control (ATC), cabin activity, procedures & documentation) will be reported for each flight period.

Samn-Perelli Scale (SP). The Samn-Perelli Scale is a commonly used 7-point scale for self-rating levels of fatigue at a given time. The scale includes: 1= fully alert – wide awake, 2= very lively, 3= okay - somewhat fresh, 4= a little tired, 5= moderately tired, 6= extremely tired, 7= completely exhausted.

Karolinska Sleepiness Scale (KSS). The KSS is a widely used 9-point scale for self-rating levels of sleepiness at a given time. The scale includes: 1 = extremely alert, 2= very alert, 3 = alert, 4= rather alert, 5 = neither alert nor sleepy, 6= some signs of sleepiness, 7 = sleepy – but no difficulty remaining awake, 8= sleepy – some effort to keep awake, and 9 = extremely sleepy – fighting sleep.

Sleep Quality rating. All sleep periods (including naps) will be rated for quality. The scale includes: 1 = extremely good, 2= good, 3 = average, 4= poor, 5 = extremely poor.

Psychomotor vigilance task (PVT). The PVT is a widely used sustained-attention, reaction-time task that measures the speed with which subjects respond to a visual stimulus. The PVT is a simple task where the subject taps the screen as soon as a visual stimulus appears. The stimulus appears randomly every few seconds during the 5-minute task.

The initial screen orients the subject to take the test in landscape mode with thumbs hovering over the screen for response (Figure 4).

Figure 4. Orientation screen shown prior to each PVT

At random intervals the counter starts running with the clock showing in the response box (Figure 5). Tapping the screen stops the counter, showing the reaction time, before the screen clears and readies for the next stimulus presentation. At the end of the test the screen will display DONE.

Figure 5. PVT screen showing response time (ms)

10. Practical Aspects of Safety and Ethical Conduct

This study is a minimal risk study. The risks associated with the protocol may differ from normal flying duties due to potential discomfort and inconvenience with wearing the actiwatch and completing tests with the PVT+ App. All participants are active-duty pilots with the appropriate clearances for flight duties. The actiwatch and iPod device housing the NASA PVT+ App are commercially available products. Participants will be informed that they may skip tests or stop the study at any time if they feel that their participation compromises flight safety. Given that the risks associated with this study are minimal, medical monitoring is not required.

11. Number, Source, and Pertinent Characteristics of Participants

Study Population. The study population does not include astronauts. All subjects will be medically qualified, active-duty flight crewmembers. Current American Airlines, United Airlines, Delta Airlines, and Southwest Airline pilots are eligible to participate in the study (pending review of other inclusion criteria, see below).

Participant Recruitment. Members of fatigue risk management teams and union representatives across each airline will distribute recruitment material via e-mail and in safety newsletters to short-haul flight crew. When feasible, members of the study team may set up study information tables in the crew rooms at airports. Participation will be completely voluntary.

Participants will not be excluded based on race, ethnicity, or gender.

Sample Size. Based on previous studies in similar studies of chronic sleep loss compared to rested performance, we expect that the effect size for PVT lapses using a 5-minute PVT will be approximately 0.75. When accounting for the clustered nature of the study (i.e., four airlines), we estimate the inter-class correlation adjustment to be .015. As such, with an alpha level of 0.05 and 80% power, we estimate that we need 18 participants per condition (night flying or circadian switches), per airline for a total sample size of 36 participants per airline. In order to account for attrition after consent, unplanned schedule changes, and incomplete data collection, we would like to recruit up to an additional 15 participants per airline. This would result in a total sample size of 204 pilots.

Inclusion/Exclusion Criteria. All medically qualified, active-duty pilots currently flying short-haul operations are eligible to be included as participants in the study. Participants must be line pilots that spend at least 50% of their typical monthly schedule flying short-haul operations (defined as flights under 6 hours duration).

All flight crew who fly short-haul operations that meet the following study inclusion criteria will be eligible for participation.

Participants must be scheduled for and willing to collect data on each of the following:

- a. Trip with Circadian Disruption: A trip containing one of the following types of WOCL infringement:

- i. *Overnight FDPs.* An FDP in which the pilot is operating one or more flights through the WOCL (0200-0559h) relative to the pilot's home-base time or clock time.

OR

- ii. *Circadian Switching.* At least one FDP that starts between 0000-0659h relative to home-base time, followed by at least one FDP that ends between 0000-0659h, or *vice versa*, within the same trip (e.g., an FDP that begins at 0500h and the next FDP ends at 0100h or *vice versa*).

AND

- b. Trip without Circadian Disruption: This trip must not contain any duties that are scheduled to begin or end between 0000h and 0659h relative to home-base time.

Proposed Test Schedule. Pending final decisions by the airlines regarding flights to be studied, the study is expected to commence in the summer of 2022.

12. Benefits of Participation

The results of this study may inform our understanding of how fatigue emerges during typical short-haul operations in the United States.

13. Possible Inconveniences, Discomfort, Pain, and Risks to the Participants

The risks associated with the protocol may differ from normal flying duties as follows:

It is possible that crew could experience slight discomfort and inconvenience from wearing an Actiwatch such as skin irritation or a rash, although no more than from wearing a wristwatch. An Actiwatch is the size of a wristwatch and is designed to be worn for weeks at a time.

Participants will record their performance using a handheld device employing the data collection app. Some crew could experience a degree of discomfort and inconvenience as the result of having their performance recorded for an extended period. Participants could be distracted from their flight duties while taking the tests, however, they will be instructed to take the test prior to the TOD, while still in the cruise phase when distractions are minimal.

Participants may also be inconvenienced by having to complete sleep, fatigue, and workload ratings. However, it is estimated that study information will only take about a total of 30 min in a day to record, with each phase of collection (e.g., pre-duty, evening diary) taking no more than 7 minutes.

As the study data will be archived at each airline or airline partner, it is possible that individual ID-coded data could be viewed or used by airline personnel.

14. Measures Taken to Minimize Discomfort and Risks

If the participant finds the actiwatch uncomfortable, then the study staff will work with the participant to determine if a different band could be used to minimize discomfort. If no acceptable alternatives are identified, then the participant will be free to discontinue wearing the device, which may require withdrawal from the study.

Participants will also be instructed to stop taking the PVT if they need to attend to their flying duties.

Participants will be informed that they are free to withdraw from the study at any time if they find the daily sleep logs and questionnaires too burdensome.

Participants will be informed that their coded data will be stored at their airline and at Washington State University. Only coded data will be archived with each airline in order to minimize the possibility that an individual's name could be linked to their data.

15. Conditions of Withdrawal from the Experiment

Participation is voluntary and pilots may choose not to participate in all or part of the study and can withdraw at any stage without being penalized or disadvantaged in any way.

16. Remuneration for Participants

All participants will be provided with NASA stickers, patches, mugs, or similar items as a token of appreciation for participation.

Compensation will be provided to participants according to the established rate for similar studies at each airline (if any).

17. Compensation in the Event of Injury

In the event of injury or illness resulting from this study and calling for immediate action or attention, NASA will provide, or cause to be provided, the necessary treatment. If eligible for California Workers' Compensation benefits while participating in this study, participants cannot sue their employer because the law makes Workers' Compensation their only remedy against their employer. Participants may have other remedies against other persons or organizations, depending on the circumstances of the injury. NASA will pay for any claims of injury, loss of life or property damage to the extent required by Federal Employees Compensation Act or the Federal Tort Claims Act.

Insurance or medical support that is normally provided to all air crew under company policy provisions at each airline will apply for study participants.

18. Consent Process

Members of fatigue risk management teams and union representatives across each airline will distribute recruitment material via e-mail and in safety newsletters to short-haul flight crew. When feasible, members of the study team may set up study information tables in the crew rooms at airports. Participation will be completely voluntary.

Interested participants will be asked to contact a research coordinator to confirm their interest and eligibility. If the participant is interested and eligible, the research coordinator will send a copy of the consent form via email for the participant to review and then schedule a time at least 24 hours later for a designated member of the research team to review the informed consent and study procedures with the participant. Informed consent will be completed by the principal investigator or a designated member of the study staff. As pilots could be based in many locations across the country, informed consent will be completed either by phone, video conference, or in person. If the informed consent session is not conducted in-person, DocuSign will be used to obtain the participant's signature and an electronic copy of the signed consent will be emailed to the participant. If the informed consent session is conducted in-person, a paper copy with wet ink signature may be collected and a photocopy will be given to the participant.

Participants may choose to withdraw from the study at any stage without being penalized or disadvantaged in any way. Participants will be told to contact the study staff if they wish to withdraw from the study. The study staff will make arrangements to collect the study equipment from the participant at their earliest convenience.

19. References

<https://ntrs.nasa.gov/citations/20060024526>

Flight and Duty Limitations and Rest Requirements: Flightcrew Members, 14 C.F.R. § 117 (2012).

Flynn-Evans, E. E., Arsintescu, L., Gregory, K., Mulligan, J., Nowinski, J., & Feary, M. (2018). Sleep and neurobehavioral performance vary by work start time during non-traditional day shifts. *Sleep Health*, 4(5), 476-484.

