Aviation regulation and safety oversight is in an era of performance-based risk management. Research is ongoing to understand the role fatigue plays in degraded human performance during various types of

operations within the aviation system. As part of this process, the Federal Aviation Administration (FAA) proposed duty limits and rest requirements which went into effect in 2014 (Code of Federal Regulations [14 CFR] Part 117, 2012). A study of fatigue in short-haul operations under these regulations is yet to be conducted. Recently, the FAA proposed the need for research to evaluate fatigue within these regulations in short-haul operations.

Determinants of Alertness and Performance in Short-Haul Aviation Operations

There has been a great deal of research to understand the influence of factors such as circadian misalignment induced by jet lag during long-haul flights on pilot fatigue and performance, but comparatively fewer studies have been conducted to evaluate fatigue and performance among pilots during short-haul operations. There are several factors that have the potential to reduce alertness and performance among airline pilots during short-haul operations, including time of day, time awake, workload, and consecutive work shifts. Each of these factors can influence a pilot's fatigue and performance, and in combination, these factors have the potential to cause severe performance impairment.

Time of Day. The circadian rhythm promotes waking during the biological day and sleep at night. When individuals who are normally awake during the day and sleep at night have to engage in night work, the sleep drive is strongest and performance is worst during the hours of 0200 to 0559, a time that has been dubbed the Window of Circadian Low (WOCL; Scientific Principles for Fatigue Management, 2015). Prior studies confirm that micro-sleeps and fatigue ratings are highest during night flights (Samel et al., 1997), whereas performance is relatively stable during short-haul flights that occur during the day when the circadian rhythm is strongly promoting wakefulness (Flynn-Evans et al., 2018).

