Start Time of Duty and Time Awake. The start time and time awake prior to a flight can also influence an individual's ability to obtain adequate sleep and maintain subsequent performance. Consecutive early work start times can lead to WOCL encroachments and lower quality sleep (Roach et al., 2012; Flynn-Evans et al., 2018), while later report times could mean pilots may wake several hours prior to their actual duty, increasing time awake before performing critical tasks (Rosekind et al., 1994; Samel et al., 1997; Gander et al., 1998; Caldwell et al., 2006; Vejvoda et al., 2014). Indeed, short-haul pilots who start work in the morning after 0900 have been shown to achieve more sleep (Roach et al., 2012; Flynn-Evans et al., 2018).

Flight Segments. Workload can also influence a pilot's fatigue level. Several studies have demonstrated that flying three or more flight segments in a single duty day is associated with increased subjective ratings of fatigue and poorer performance (Bourgeois-Bougrine et al., 2003; Powell et al., 2007; Honn et al., 2016).

Consecutive Operations. Several studies have demonstrated that working consecutive days is associated with poorer performance. For example, Flynn-Evans et al. (2018) found that pilots performed worse with each consecutive day of flying when scheduled for early starts, long midday flights, and late finishing daytime flights.

Preliminary Data: Focus Group Study

In order to identify fatigue factors of greatest importance to study, we conducted a series of focus groups across four major commercial passenger airlines in the United States. This study revealed several

operations that pilots identified as fatiguing (Table 1). We combined these themes into six over-arching categories including: circadian disruption, high workload, rest opportunity, schedule changes, regulations, and long sits. While categories provide a useful summarization of the overall content, the value of the qualitative approach is the resolution of data at theme and code level. Therefore, core *themes* and CODES contributing to these categories are described below.

Table 1. Themes ranked by frequency of codes within each theme.

Theme	N	%
Circadian switches	171	10.5
Rest duration (layover)	153	9.4
High workload / Hassle factors	151	9.3
Number of flights	121	7.4
FAR 117 issues	93	5.7
Long sits	85	5.2
Redeyes	83	5.1
Unpredictability	79	4.9
Aircraft & crew swaps	73	4.5
Rest timing	73	4.5
Out-of-hours work	68	4.2
Early duties	64	3.9

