It is difficult to study the impact of so many factors on fatigue because the series of flights that pilots are scheduled for, known as a trip, can include factors that make data aggregation difficult without an enormous sample size. As a result, it is necessary to collect data on targeted operations in order to evaluate the impact of the most disruptive factors on fatigue. Hence, our primary aim is to compare sleep, sleepiness, performance, and workload during trips *with* circadian disruption to trips *without* circadian disruption. We will collect observational data on the other factors that were identified in the focus groups in order to help inform future research in those areas. We will study participants during their normal scheduled operations.

6. Why Human Research is Required

Human research is required because there are no other reliable, efficient, and cost-effective methods for obtaining such information from animal or modeling sources. Only performance by humans is possible or relevant.

7. Conflict of Interest

Do any of the participating study investigators or other research personnel (or their immediate family/significant other) have a financial and/or intellectual property interest in the sponsor or products used with this project?

____ Yes No

8. Plan of Study

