8.1 Protocol Overview

Scientific Merit. Please see attached ARC476 for scientific review and approval.

Specific Aims. The goal of this study is to provide insight into the influence of trips including circadian disruption on pilot cognitive performance, fatigue, sleepiness, sleep, and workload during short-haul operations across multiple airlines.

Hypotheses.

We aim to study pilots completing trips that include circadian disruption compared to trips that do not include circadian disruption.

- We hypothesize that cognitive performance, fatigue, sleepiness, and sleep outcomes will be worse during circadian disrupted trips compared to trips that do not involve circadian disruption.

Primary Outcome Measures.

Objective cognitive performance will be measured by the **psychomotor vigilance task (PVT)**, a simple reaction time task with outcome measures including mean reaction time, response speed (1/reaction time) and number of lapses (reaction time >500 ms). PVT performance will be measured at, or near, the timing of top of descent (TOD) during each flight.

Statistical Analyses.

The following factors will be also considered for inclusion in the analysis:

- **Schedule features:** flight duration, duty duration, duty start and finish times
- **Individual factors:** age, experience, chronotype (as measured by the morningness-eveningness questionnaire), sleep need
- **Sleep:** sleep duration, sleep loss, sleep start and finish times (all measured by the actiwatch)
- **Fatigue/alertness:** pre- and post-sleep and on-duty fatigue and alertness ratings (as measured by subjective scales)
- **Workload:** hassle factors encountered during flights and NASA TLX

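### Is the sample size undermined by taking its effect size of 0.75 from chronic sleep loss studies, when a 2-7 day trip can qualify through one overnight duty?

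*Protocol*

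**What the plan says.** Section 11, Sample Size, takes its expected effect from previous research into "chronic sleep loss compared to rested performance, we expect that the effect size for PVT lapses using a 5-minute PVT will be approximately 0.75". It then allows for airlines: "When accounting for the clustered nature of the study (i.e., four airlines), we estimate the inter-class correlation adjustment to be .015". With alpha 0.05 and 80% power it concludes that "we need 18 participants per condition (night flying or circadian switches), per airline for a total sample size of 36 participants per airline". An allowance of up to 15 more per airline gives 204 pilots.

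In the inclusion criteria of the same section, the disrupted trip is "A trip containing one of the following types of WOCL infringement". Route i is an overnight flight duty period (FDP) flown through the window of circadian low; by its wording one is enough. Route ii is a switch between early-starting and late-ending duties and needs at least two FDPs. Each pilot also flies a trip without disruption (criterion b; Table 2). Section 9 gives trips of 2-7 days, and section 8.1 places the primary PVT near top of descent on each flight.

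On the level of analysis, section 8.1 states one overall hypothesis, and its aim covers "workload during short-haul operations across multiple airlines". Section 8.6 has coded data from all airlines aggregated at one site for processing and analysis.

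**The concern.** The source contrast and the trial contrast differ. Chronic sleep loss against rest is a sustained exposure; a week-long trip with one overnight duty may consist mostly of ordinary flights, each with its own PVT. Section 5 of the protocol says that "performance is relatively stable during short-haul flights that occur during the day when the circadian rhythm is strongly promoting wakefulness", which suggests that those flights could pull the trip-level effect below 0.75. One figure also serves both conditions, night flying and circadian switches, without a reason given for either.

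In addition, the 80% power is attached to no named comparison. The 18 is quoted per condition and per airline, so a reader could take it as the size of a test inside each airline. If that were the plan and the true effect were smaller, such a test would have little power, and a null result in one airline might be read as absence of harm.

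**Working it through.** **Inputs from section 11:** effect 0.75, alpha 0.05, power 80%, ICC 0.015, 18 pilots per condition per airline, four airlines, two conditions.

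**Assumptions, not stated there:** alpha is two-sided; 0.75 is in standard deviations of the within-pilot difference; the cluster size in the design effect is 18, or 36 when both conditions are pooled.

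**Step 1: reproduce the 18.** Paired comparison, normal approximation:

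- n = (1.960 + 0.842)² / 0.75² = 7.849 / 0.5625 = 13.95
- design effect = 1 + (18 - 1) x 0.015 = 1.255
- 13.95 x 1.255 = 17.5, so 18
- total = 4 x (36 + 15) = 204

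Both figures stand. A two-sample calculation gives 28 per group before inflation and 36 after it (28 x 1.255 = 35.1), so with two-sided alpha the 18 points to the within-pilot reading.

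**Step 2: which comparison does the power serve?** A between-airline ICC matters only when airlines are combined. Section 8.1 has a single hypothesis and an aim across airlines, and section 8.6 aggregates the data for analysis. No section announces a test within an airline. The per-condition, per-airline count then reads as a recruitment allocation.

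**Step 3: how small an effect do the planned numbers support when pooled?** Two-sided paired t, noncentrality d x √(n / design effect), n - 1 degrees of freedom. For all 144 pilots the larger design effect is used: 1 + 35 x 0.015 = 1.525.

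| Comparison | Pilots | Design effect | Detectable at 80% | Share of 0.75 |
|---|---|---|---|---|
| One condition, four airlines | 72 | 1.255 | 0.375 | 0.50 |
| Both conditions | 144 | 1.525 | 0.290 | 0.39 |

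Power if the trip-level effect is only part of 0.75:

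| Trip-level effect | 72 pilots | 144 pilots |
|---|---|---|
| 0.5625 (75%) | 99% | about 100% |
| 0.375 (50%) | 80% | 95% |
| 0.30 (40%) | 61% | 82% |
| 0.25 (33%) | 46% | 67% |

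**Step 4: the single-airline reading.** With 18 pilots and the design effect of 1.255, a paired t-test detects 0.785 with 80% power, which seems to leave no room below 0.75. Two things produce that figure:

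- The design effect describes variation between airlines. Inside one airline there is one cluster and nothing between airlines to inflate.
- The 18 was obtained with the normal approximation. On that basis, even with 1.255, the detectable effect is 2.802 x √(1.255 / 18) = 0.74.

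Without the inflation, the paired t-test with 18 pilots detects 0.70 and has 85% power at 0.75.

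**Step 5: does the document show that 0.75 is too large?** Assuming one FDP per day, the minimum qualifying FDPs make up 1/7 to 1/2 of a trip under route i (14-50%) and 2/7 to 2/2 under route ii (29-100%). These are minimum exposures and do not translate into an effect size. Carry-over to later duties is not known, and averaging over more flights also lowers the noise in a trip mean. The background does not settle the direction. The sentence on stable daytime performance also says that micro-sleeps and fatigue ratings are highest on night flights. Section 5 further reports that "pilots performed worse with each consecutive day of flying when scheduled for early starts, long midday flights, and late finishing daytime flights". That is build-up over days, and since it covers daytime duties it could occur on both kinds of trip. The studies behind 0.75 are not identified, so their likeness to these schedules cannot be judged from the document.

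**The case for a change.** The strongest case for the concern is that the protocol itself chose the effect, its source, the ICC and the number, so the reasoning belongs there and not only in an SAP. Section 11 does not argue why a chronic sleep loss effect should hold for a trip with one overnight duty, gives no separate reason for each condition, does not state the units of 0.75 and does not name the comparison that carries the 80%. All of that is true.

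Dilution could also be severe. Suppose one FDP per day with equal numbers of flights, the full 0.75 on the overnight duty only, no carry-over, and an unchanged standard deviation of the trip mean. One affected duty in seven then gives 0.75 / 7 = 0.107, and power is about 13% for one condition and 18% over all pilots (normal approximation). This extreme needs every one of those assumptions together with the longest trip and the minimum exposure. Nothing in the protocol supports them as the typical case. The same arithmetic for a 2-day trip gives 0.375, which the pooled numbers carry.

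Section 5 also recognises the problem of mixed trips and gives its answer: "it is necessary to collect data on targeted operations in order to evaluate the impact of the most disruptive factors on fatigue". What remains is a thin justification. A fuller sentence would help a reader, but it would correct no figure and change no recruitment number.

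**Conclusion.** The concern does not hold. The 18 and the 204 reproduce, the 80% power is not shown to be wrong, and any shortfall of the trip-level effect below 0.75 cannot be computed from the document. The level of comparison is not stated in so many words but can largely be read as pooled over airlines. On that reading the planned numbers keep 80% power down to half of 0.75 in each condition and to about 39% of it over both. The apparent lack of margin within one airline comes from a misapplied design effect and a change from normal to t calculation, for a test that no section plans. Naming the level and the trip summary is detail commonly left to an SAP.

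This rests on two-sided alpha, on 0.75 being a within-pilot standardized difference, and on the cluster sizes used above. If the true trip-level effect were a third of 0.75 or less, pooled power would fall below 70%, but nothing in the document indicates that it is.
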